### **5.6 STRATEGIES FOR RECRUITMENT**

This is a multi-site study and subjects will be enrolled at the NIH Clinical Center, Inova Fairfax and Alexandria hospitals. Hospitalized participants will be recruited from within NIH and from the Inova hospitals.

A written strategic recruitment plan will be authored by the NHLBI Patient Recruitment Office (PRO) and ongoing regular recruitment-focused meetings will be held with the PRO and study staff and partners to ensure the study is meeting enrollment projections. If enrollment projections

*Abbreviated Title: Fostamatinib for COVID*

*Version Date: 09/17/2020*

are not being met, a strategy to boost enrollment will be implemented, and may include local news media coverage and live social media events.

Source of participants include inpatient hospital setting, outpatient clinics, and general public. The participants may also be recruited via self-referral, from in-patient services of regional hospitals and from outpatient settings.

Participants may be recruited through the use of:

- Flyers, documents/info cards, etc. for in-hospital use with patients and family;
- Recruitment advertisements and writeups placed in the NIH Record, NIH websites, the Clinical Center News;
- ResearchMatch.org;
- Newspaper writeups (print and digital) in local newspapers or outlets;
- NIH email listservs;
- Media interviews with investigators;
- NIH social media on Facebook and/or Twitter;
- ClinicalTrials.gov, Clinical Center “Search the Studies” website, NHLBI website, and NIH CC study recruitment page facilitated by CC communications office;
- Paid, targeted advertising, including digital social media ads, to local public population may be done led by the NHLBI digital communications specialist.
- A letter to physicians about the study may be provided to area ICUs and hospitalist groups.
- Hospital partners will be provided with written study materials, and in-service sessions by the study PI to educate and inform about the study.

There are no restrictions based on gender, race or ethnicity, or non-English speaking subjects.

All advertising/recruitment language will be IRB reviewed/approved prior to posting/using. Recruitment materials may be translated from English into other languages, including Spanish. Anticipated accrual rate is approximately 25 patients per month.

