## **6.3 MEASURES TO MINIMIZE BIAS: RANDOMIZATION AND BLINDING**

### **6.3.1 Randomization**

The study will randomize subjects 1:1 to placebo or fostamatinib. Once a subject has completed the screening and baseline period and evaluation for inclusion/exclusion criteria, the randomization process will begin. The site investigator or designee will obtain the randomized assignment for that subject from the data coordinating center. Randomization will be stratified by site and severity of illness at enrollment. Severity of illness will be stratified into ordinal scale 5 and 6 (supplemental oxygen via nasal canula or non-invasive ventilation), mechanical ventilation, and ECMO.

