## **9 STATISTICAL CONSIDERATIONS**

### **9.1 SAMPLE SIZE DETERMINATION**

This study plans to enroll approximately 60 eligible subjects, randomized in a 1:1 ratio to fostamatinib or placebo.

The primary outcome of the study is cumulative incidence of SAEs through day 29. Because of data on safety of the fostamatinib in combination with standard of care is unavailable, the sample size is determined by the feasibility to assess the activity and safety of the study treatment in a diverse group of hospitalized adults. As background standards of supportive care may evolve/improve over time as more is learned about successful management of COVID-19, comparisons of safety will be based on data from concurrently randomized subjects between fostamatinib and placebo arm. Randomization is essential to evaluate the safety and early efficacy of fostamatinib, which may lead to generalizable evidence of future confirmative studies.

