#### **9.3.3 Analysis of the Secondary Endpoint(s)**

To determine a subject's clinical status using the ordinal scale: On Day 1, report their clinical status at enrollment (start of study drug). On Day 2, report the period from enrollment to midnight on Day 1. On Day 3 through Day 11, or until discharged, and on Days 15, 22 and 29, provide the worst clinical assessment for the previous day (i.e., midnight to midnight; 00:00 –

23:59 (24-hr clock)). For example, on study Day 3 when completing the form, the worse clinical outcome measure of Day 2 is captured with the worst being death followed by ECMO, mechanical ventilation, etc. The Day 2 measurement is assessed as occurring anytime in that 24-hour period (00:00 to 23:59).

Secondary endpoints will be evaluated as follows:

1) The time to recovery by Day 29, it will be estimated by median and 95% confidence interval by study arm. The cumulative recovery rate will be estimated by the Kaplan-Meier method. The comparison between two treatment arms will be assessed by the log-rank test. The recovery ratio and hazard ratios will be based on the Cox model. The analysis will be stratified by disease severity at enrollment.

The time to recovery will be evaluate and censored up until Day 29. It is defined as the elapsed time in days from the day 1 to the earliest day at which a subject reaches recovery (having 1-3 of the 8-point ordinal scale). Any subjects that are lost to follow-up prior to an observed recovery will be censored at the day of their last observed assessment. Subjects who complete follow-up but do not experience recovery will be censored at Day 29. All deaths within Day 29 (and prior to recovery) will be considered censored at Day 29. Analysis will be based on intention to treat including all randomized patients. Patients who have received at least four doses of study drug will be considered in a sensitivity analysis for this secondary outcome.

2) Duration of events (e.g., mechanical ventilation or days in the ICU) will be summarized with median and interquartile rage by the study arms and compared between the treatment arms by Wilcoxon's rank sum test or log-rank test.

3) Binary events (e.g., need for intubation) will be summarized as percentages and 95% confidence intervals by the study arms and compared between the treatment arms by Fisher's exact test.

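### Randomisation is stratified by site and severity, but the time-to-recovery analysis uses severity only, which costs some efficiency if sites differ in recovery

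*Combined protocol and SAP*

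**What the plan says.** Section 6.3.1: "Randomization will be stratified by site and severity of illness at enrollment". The severity levels follow: "Severity of illness will be stratified into ordinal scale 5 and 6 (supplemental oxygen via nasal canula or non-invasive ventilation), mechanical ventilation, and ECMO".

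Section 9.3.3, item 1, covers time to recovery by Day 29. The test: "The comparison between two treatment arms will be assessed by the log-rank test". The estimate: "The recovery ratio and hazard ratios will be based on the Cox model". The only stratification: "The analysis will be stratified by disease severity at enrollment". It does not say which grouping of severity is meant.

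Site is neither a stratum nor a covariate in any section 9 analysis, and it is not a subgroup in section 9.3.7. No reason is given.

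On sites, section 5.6 says "subjects will be enrolled at the NIH Clinical Center, Inova Fairfax and Alexandria hospitals", and the synopsis allows for expansion to another site. Whether the two Inova hospitals count as one site or two is not stated, so site has at least two or three levels.

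**The concern.** A factor that was important enough to balance at randomisation is normally carried into the analysis. If it predicts outcome and is left out, the arms are more alike than the analysis assumes. The test then rejects too rarely, and the Cox hazard ratio shrinks towards 1.

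The documents give two reasons why recovery could vary by site:

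- Recovery means ordinal score 1 to 3. Scores 1 and 2 are both out of hospital, and score 2 allows home oxygen. Score 3 is for stays prolonged for infection control. For most patients recovery is therefore likely to coincide with discharge, which depends partly on hospital practice.
- The standard-of-care text in section 4.1 permits additional medicines at a site whose own standard changes.

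At stake are some power and some dilution of the estimated effect on the first-listed secondary endpoint, in a phase 2 trial meant to inform later studies.

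**Working it through.** **1. No figure to reproduce.** Section 9.1 says "This study plans to enroll approximately 60 eligible subjects, randomized in a 1:1 ratio to fostamatinib or placebo" and that "the sample size is determined by the feasibility to assess the activity and safety of the study treatment". It gives no alpha, power, effect size or event count for this endpoint. For orientation only, Schoenfeld power = Φ(√d/2 × ln HR − 1.96). With d = 45 recoveries and HR 2 this is Φ(3.354 × 0.693 − 1.96) = Φ(0.365) = 64%. With HR 1.5 it is Φ(3.354 × 0.405 − 1.96) = 27%.

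**2. Simulation inputs.** From the documents: N = 60, 1:1 allocation, randomisation stratified by site and three severity levels, cut-off at Day 29. Assumed: two-sided alpha 0.05; blocks of 4; treatment HR 2; severity mix 75/20/5%; relative recovery hazards 1/0.35/0.2; 79% recovery by Day 29 in control patients at scale 5-6 at an average site; deaths and dropout not modelled separately. The site ratio is the recovery hazard at the fastest site over that at the slowest. There were 1,200 trials per power setting (Monte Carlo error of a single power figure √(0.6 × 0.4/1200) = 1.4 points).

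**3. Methods compared.** The stratified log-rank statistic is Z = Σ(O − E)/√ΣV, summed over strata and rejecting at |Z| > 1.96. The Cox model has hazard h_s(t)·exp(βA + γ·site) with severity strata s and a Wald test of β. Power is in %; the last column is the mean estimated β without and with site (true value ln 2 = 0.693).

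| Sites | Site ratio | Log-rank, severity | Log-rank, site × severity | Cox, severity | Cox, severity + site covariate | Mean β |
|---|---|---|---|---|---|---|
| Two, 50/50 | 1 | 64.2 | 62.4 | 61.5 | 62.2 | 0.68 → 0.69 |
| | 1.5 | 61.8 | 61.4 | 59.1 | 60.8 | 0.66 → 0.68 |
| | 2 | 56.9 | 59.8 | 53.8 | 58.6 | 0.62 → 0.68 |
| | 3 | 48.9 | 59.8 | 45.1 | 58.3 | 0.57 → 0.68 |
| Three, 20/40/40 | 1 | 66.4 | 61.8 | 62.2 | 63.8 | 0.68 → 0.70 |
| | 1.5 | 63.8 | 60.6 | 59.1 | 62.3 | 0.67 → 0.70 |
| | 2 | 60.4 | 60.9 | 56.6 | 60.4 | 0.64 → 0.69 |
| | 3 | 56.9 | 60.5 | 53.1 | 60.2 | 0.61 → 0.69 |

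**4. Size of the loss.** Log-rank against log-rank:

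- Twofold: 59.8 − 56.9 = 2.9 points with two sites and 60.9 − 60.4 = 0.5 with three. A 20/80 split gives 64.2 − 60.8 = 3.4.
- Threefold: 10.9, 3.6 and, for the 20/80 split, 63.1 − 54.4 = 8.7.

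A second model (30% at scale 7, 12% never recovering, severity as 5-6 versus 7) gave 40.3 − 37.9 = 2.4 and 39.2 − 32.7 = 6.5 with two sites, and 1.1 and 3.2 with three equal sites. Together this is about 1 to 4 points at twofold and 3 to 11 at threefold. Cox against Cox the differences are somewhat larger: 3.8 to 4.8 at twofold and 7.1 to 13.2 at threefold in the table, and 3 to 4 and 5 to 7 in a further simulation.

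**5. Full site-by-severity strata.** With three similar sites they lose power: 61.8 − 66.4 = −4.6 at ratio 1 and 60.6 − 63.8 = −3.2 at 1.5. Three severity levels and two or three sites make 6 to 9 cells. At the assumed 5% on ECMO, 60 × 0.05 = 3 patients would be spread over two or three of them. With severity as two levels the second model still lost 1.6 points at ratio 1.

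**6. Null rejection rates.** The severity-only log-rank test rejected in about 4 to 5% of null trials at ratios 2 to 3. For Cox, severity only → with site: two sites 3.8 → 4.2% (ratio 1.5) and 2.9 → 4.7% (ratio 3); three sites 3.2 → 3.8% and 3.7 → 5.1%. Across all simulations the site-covariate model lay at about 4 to 6.5%.

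**The case against.** The strongest reply is that this is a legitimate choice of parsimony. The plan already stratifies by severity, plausibly the stronger prognostic factor. No document shows that sites differ, and if they do not, nothing is lost. With three sites the log-rank gain is about 1 point or less at twofold, and full stratification loses power when sites are alike. Part of any gain comes with a higher rejection rate under the null. The primary endpoint is SAEs, and time to recovery is one of 13 secondary endpoints.

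Most of this stands. It limits the size of the point and rules out full site-by-severity strata as the remedy. It does not explain why a recorded randomisation factor is used nowhere, and with site as a single covariate the sparse-cell objection largely falls away.

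A reader might infer three stronger things that the documents do not support:

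- **The recovery test is invalid.** The effect runs the other way: the test becomes conservative.
- **The trial loses power it was designed to have.** Section 9.1 sets the size by feasibility and claims no power.
- **Sites do differ, and widely.** At a fivefold difference the simulated log-rank loss reaches 12 to 24 points, but nothing in the documents points to a difference of that size.

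**Conclusion.** The mismatch between sections 6.3.1 and 9.3.3 is real and the direction of its effect is clear: conservative, with the hazard ratio drawn towards 1. Its size is conditional on an unknown site difference. It is negligible below about twofold, about 1 to 4 power points at twofold and about 3 to 11 at threefold. With two equal sites the mean hazard ratio falls from about exp(0.68) = 1.97 with site in the model to exp(0.62) = 1.86 at twofold and exp(0.57) = 1.77 at threefold.

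These figures rest on an assumed treatment hazard ratio of 2, an assumed severity mix and recovery rates, and two or three sites. This is a worthwhile small improvement to one secondary analysis. It does not threaten the trial's validity or its primary endpoint.

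**What to change.** In section 9.3.3, item 1, replace the stratification sentence with wording to this effect: the recovery ratio, its confidence interval and its test come from a Cox model stratified by baseline severity (scale 5-6 versus 7) with site as a covariate; a log-rank test stratified by severity is supporting.

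- State that mechanical ventilation and ECMO are merged because ECMO is likely to be sparse. This departs from the three randomisation levels but follows the ordinal scale.
- State whether the Inova hospitals are one site or two.
- Do not use full site-by-severity strata, and do not let the data choose between models.
- Name the test statistic. In the table, the Wald test with site trails the planned log-rank test by 64.2 − 62.2 = 2.0 points (two sites) and 66.4 − 63.8 = 2.6 (three) when sites are alike. Much of that comes from the Wald statistic, since the score test of the severity-stratified Cox model without site is essentially the log-rank test. A score or likelihood-ratio test is the natural choice.

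The cost is one sentence settled before unblinding, one or two extra parameters, and a null rejection rate about 0 to 2 points above that of severity alone. Site is already recorded for randomisation. If site was left out on purpose, a sentence giving the reason would also close the point.

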## 1 PROTOCOL SUMMARY

### 1.1 SYNOPSIS

**Title:** **A Phase II Study Evaluating Fostamatinib for Hospitalized Adults with COVID-19**

**Study Description:** This is a randomized, double-blind, placebo-controlled trial of fostamatinib for the treatment of hospitalized patients with COVID-19.

We will randomly assign fostamatinib or matched placebo (1:1) to approximately 60 eligible COVID-19 patients who are a 5 to 7 on the 8-point scale (requiring supplemental oxygen via nasal canula or non-invasive ventilation, requiring mechanical ventilation or extracorporeal membrane oxygenation).

**Objectives:** The primary objective of this study is to evaluate the safety of fostamatinib for the treatment of hospitalized patients with COVID-19.

Secondary objective will be to assess the early efficacy and clinically relevant endpoints of disease course

Exploratory objective will be to study the host immunological response to COVID-19 and potential mechanism of action of fostamatinib

**Endpoints:** The primary endpoint is cumulative incidence of SAEs through day 29.

Secondary endpoints are:

1. Time to recovery: day of recovery is defined as the first day on which the subject satisfies one of the following three categories by Day 29:  
Ordinal scale 3: hospitalized, not requiring supplemental oxygen-no longer requiring ongoing medical care;  
Ordinal scale 2: non-hospitalized, limitations on activities and/or requiring home oxygen  
Ordinal scale 1: non-hospitalized, no limitations on activities
2. Number of days free of mechanical ventilation [patients with baseline ordinal scale 5-6 only]
3. 14-day and 28-day mortality
4. Grade 3 and 4 AE through day 60.
5. Days of hospitalization
6. Ordinal scale at day 15 and day 29

7. Change in CRP, IL-6, d-dimer, ferritin, fibrinogen, absolute lymphocyte count, absolute neutrophil count, and platelet count from baseline [day 3, 5, 8, 11, 15, 29]
8. Number of days in the ICU [entire hospitalization]
9. Relative change in PaO2/FiO2 or SpO2/FiO2 ratio
10. Change in SOFA score from baseline (day 1) [day 3, 5, 8, 11, 15, 29]
11. Number of days on oxygen (Including nasal canula, non-invasive, and mechanical ventilation)
12. Days free of renal failure [entire hospitalization]
13. Clinically relevant deep vein thrombosis (DVT) or pulmonary embolism (PE) [entire hospitalization]

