## 3 OBJECTIVES AND ENDPOINTS

The primary objective of this study is to evaluate the safety of fostamatinib for the treatment of hospitalized patients with COVID-19.

OBJECTIVES	ENDPOINTS	JUSTIFICATION FOR ENDPOINTS
Primary		
To assess the safety of fostamatinib in hospitalized patients with COVID-19	Cumulative incidence of SAEs through day 29.	This endpoint was chosen to evaluate the safety of fostamatinib for the treatment of hospitalized patients with COVID-19.
Secondary		

*Abbreviated Title: Fostamatinib for COVID*

*Version Date: 09/17/2020*

OBJECTIVES	ENDPOINTS	JUSTIFICATION FOR ENDPOINTS

To assess the effect of fostamatinib on clinically relevant endpoints of disease course
	
 
1. Time to recovery by day 29: day of recovery is defined as the first day on which the subject satisfies one of the following three categories: Ordinal scale 3: hospitalized, not requiring supplemental oxygen-no longer requiring ongoing medical care; Ordinal scale 2: non-hospitalized, limitations on activities and/or requiring home oxygen; Ordinal scale 1: non-hospitalized, no limitations on activities
 
2. Number of days free of mechanical ventilation [patients with baseline ordinal scale 5-6 only]
 
3. Mortality at day 14 and 28
 
4. Grade 3 and 4 AE through day 60
 
5. Days of hospitalization
 
6. Ordinal scale at day 15 and day 29
 
7. Change in CRP, IL-6, ferritin, d-dimer, fibrinogen, absolute lymphocyte count, absolute neutrophil count, and platelet count from baseline [day 3, 5, 8, 11, 15, 29]
 
8. Number of days in the ICU [entire hospitalization]
 
9. Relative change in PaO2/FiO2 or SpO2/FiO2 ratio
 
10. Change in SOFA score from baseline (day 1) [day 3, 5, 8, 11, 15, 29]
 
11. Number of days on oxygen (Including nasal canula, HFNC, non-invasive, and mechanical ventilation)
 
12. Days free of renal failure [entire hospitalization]
 
	
Each of the secondary clinical endpoints were deemed to be clinically relevant indicates for improved or worsening disease course

*Abbreviated Title: Fostamatinib for COVID*

*Version Date: 09/17/2020*

OBJECTIVES	ENDPOINTS	JUSTIFICATION FOR ENDPOINTS

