## 4 STUDY DESIGN

### 4.1 OVERALL DESIGN

We intend to study fostamatinib for the treatment of hospitalized patients with COVID-19.

- This will be a multicenter, randomized, double-blind, placebo-controlled, phase 2 trial with the objective to evaluate the safety of fostamatinib compared to matching placebo in COVID-19 patients who are hospitalized with a 5, 6, or 7 on the 8-point ordinal scale.
- The NHLBI will be the Coordinating Center for this multicenter study. All participating sites will enroll and treat subjects as described below. Research labs for exploratory endpoints will be processed at participating sites or shipped to the NIH Clinical Center for processing.
- All study participants will receive standard of care throughout the entire study and then will be randomized to 150 mg of fostamatinib twice a day or placebo for 14 days (total 28 doses).
- Subjects will be assessed daily while hospitalized and followed until day 60. If patients improve and are discharged prior to day 14 the study drug will be continued until day 14 as an outpatient. Patients who are discharged on study drug will receive a phone call daily to assess for adverse events and will have safety labs drawn on days 3, 5, 8, 11 as applicable (outpatient third party lab acquisition may be utilized as needed). We will make every effort to bring back discharged patients for outpatient visits on days 15, 22, 29, and 60 to include laboratory draws. In patients who are unable to follow-up, they will receive a telephone visit as a follow up.
- Day 1 of study is the first day of study drug and patients will be followed until day 60.

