4) Mortality rate and the time to event endpoints will be estimated by Kaplan-Meier method and 95% confidence intervals by study arm and compared between the treatment arms by log-rank test.

5) Longitudinal measurements of each biomarker variables will be plotted over time. The mean and percent change from baseline for each variable will be estimated and compared to study arm using appropriate parametric or nonparametric tests and regression modeling.

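### The log-rank test for 14- and 28-day mortality has no stated strata, cut-off day or fixed-day contrast; unstratified it is modestly conservative, and run to Day 60 it answers a different question

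*Combined protocol and SAP*

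**What the plan says.** - **Endpoint.** The Synopsis (1.1) lists "14-day and 28-day mortality"; the objectives table (section 3) has "Mortality at day 14 and 28".
- **Analysis.** Section 9.3.3 item 4 reads "Mortality rate and the time to event endpoints will be estimated by Kaplan-Meier method", adds 95% confidence intervals by arm, and then has the arms "compared between the treatment arms by log-rank test". It gives no strata, horizon, censoring rule or between-arm contrast at Day 14 or Day 28.
- **Neighbouring items.** For time to recovery, item 1 says "The analysis will be stratified by disease severity at enrollment" and "The time to recovery will be evaluate and censored up until Day 29". Item 3 assigns Fisher's exact test to binary events, a class that could also take in death by a fixed day.
- **Randomisation.** Section 6.3.1: "Randomization will be stratified by site and severity of illness at enrollment". It lists three severity levels: scale 5–6, mechanical ventilation, and ECMO.
- **Follow-up.** Section 4.1: "Day 1 of study is the first day of study drug and patients will be followed until day 60". In the schedule of activities (1.3), footnote c has mortality asked about at the Day 15, 22, 29 and 60 contacts.
- **Size.** Section 9.1 sets about 60 patients, 1:1, by feasibility, with no alpha, power or effect size for mortality.

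**The concern.** There are two separate issues.

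First, a log-rank test compares the death rates of the two arms over its whole horizon. It does not compare mortality at a given day, and one p-value cannot serve both Day 14 and Day 28. Because item 4 sets no horizon and deaths are collected to Day 60, several different tests would all comply with the text, including Fisher's test under item 3. The choice could be made after the data are seen.

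Second, stratified randomisation balances the arms on severity, so the arm difference varies less between repeated trials than an unstratified test assumes. If severity is prognostic, the true type I error falls below nominal. The protocol's own background figures (2.3.3) point to a strong factor: control mortality of 40.7% in ventilated patients against 24.6% overall in the dexamethasone trial.

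At stake is the mortality comparison in a trial where the simulations below expect roughly 11 to 15 deaths by Day 28 in all but an extreme scenario.

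**Working it through.** **1. The plan's own figure.** There is none to reproduce, because the sample size is set by feasibility. For context, take 30 per arm and the ventilated-patient rates in 2.3.3, 40.7% and 29.0%. Power = Φ[(|p1 − p0| − 1.96·SE0)/SE1].
- SE0 = √(2 × 0.3485 × 0.6515/30) = 0.1230
- SE1 = √((0.407 × 0.593 + 0.290 × 0.710)/30) = 0.1221
- Power = Φ[(0.117 − 0.2411)/0.1221] = Φ(−1.017) ≈ 15%. The same formula needs 260 per arm for 80%.

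If both arms had 24.6% mortality, the 95% interval for the difference would have half-width 1.96 × √(2 × 0.246 × 0.754/30) = 1.96 × 0.111 = 21.8 points.

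**2. Simulation set-up.** From the documents: 60 patients, 1:1, allocation stratified by severity and site, 40.7% mortality for ventilated patients, follow-up to Day 60. Assumed: two-sided 5% level, severity mix, the other mortality rates, two sites, blocks of 4, exponential death times in whole days, no dropout, and hazards after Day 28. There were 4,000 trials per null scenario (Monte Carlo error √(0.05 × 0.95/4000) = 0.3 points) and 3,000 per alternative (√(0.35 × 0.65/3000) = 0.9 points).

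**3. Type I error, horizon Day 28.**

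| Severity mix | Assumed Day 28 mortality | Unstratified | Stratified by severity |
|---|---|---|---|
| 70/30 | 15% / 40.7% | 4.2% | 5.3% |
| 50/50 | 10% / 40.7% | 3.6% | 4.8% |
| 60/30/10 (ECMO separate) | 10% / 40.7% / 70% | 3.2% | 5.6% |
| 50/50, extreme | 5% / 70% | 1.0% | 4.9% |

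A second setting (30% at scale 7; mortality 10% and 45%; 3,000 trials) gave 3.4–3.5% against 4.9–5.5%.

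**4. Power to Day 28.** With hazard ratio 0.35 (60/30/10; 15%, 40.7%, 60%), power is 35% unstratified and 38% stratified. In the second setting with hazard ratio 0.25 it is 37–39% and 41–43%. Fisher's exact test at Day 28 had 27% power in the first setting, and type I error of 1.9–2.5% in the first three null scenarios.

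**5. Effect of the horizon, unstratified test.**

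| Hazard ratio to Day 28 | After Day 28 | Late hazard ÷ early hazard | Power to Day 28 | Power to Day 60 |
|---|---|---|---|---|
| 0.35 | 0.35 | 0.5 | 35% | 47% |
| 0.35 | 1 | 0.5 | 35% | 19% |
| 0.35 | 1 | 1.0 | 35% | 14% |
| 0.35 | 2 | 0.5 | 35% | 5% |
| 0.25 | 0.25 | 0.5 | 39% | 52% |
| 0.25 | 0.25 | 0.25 | 41% | 49% |
| 0.25 | 1 | 0.25 | 38% | 24% |
| 0.25 | 1 | 0.1 | 40% | 32% |

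The direction follows from the event counts. With no late effect, the expected test statistic is multiplied by √(deaths to Day 28 ÷ deaths to Day 60). With a persistent effect it is multiplied by the inverse. In the first two rows there are 11.5 early deaths on average, and 16.4 (persistent) or 19.0 (no late effect) in total. The factors are √(16.4/11.5) = 1.19 and √(11.5/19.0) = 0.78. A power of 35% corresponds to an expected statistic of 1.960 − 0.385 = 1.575. Scaling gives 1.88 (power about 47%) and 1.23 (about 23%), close to the simulated 47% and 19%.

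**The case against.** A reader might infer that the plan commits to an unstratified test over all 60 days and must therefore lose power. The documents do not support that. Item 4 is silent on strata and horizon. A log-rank test stratified by severity and censored at Days 14 and 28 would comply, and the endpoint itself names those days. Nor is a loss from late deaths inevitable: step 5 shows a gain when the effect persists and a shrinking loss as late deaths become rarer. The documents give no late mortality with which to choose between these cases.

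It can also be said that:
- the Kaplan-Meier estimates with intervals by arm can be read at Days 14 and 28, so the estimation already fits the endpoint;
- the conservatism guards against false positives and costs only a few points of power;
- mortality is one of 13 secondary endpoints in a feasibility-sized trial, so no confirmatory claim hangs on this p-value;
- an ECMO stratum may be nearly empty (at 10% of 60, about 6 patients), and stratifying on it is not free: the three-level scenario has the highest stratified error, 5.6%.

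All of this stands, and it limits the point to the test and the missing between-arm contrast. It does not remove the point. Item 1 shows that the authors considered both features necessary for a time-to-event comparison, and item 4 leaves them open where the answer changes the result.

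**Conclusion.** The point holds as a gap in specification with a small, demonstrable statistical cost. Item 4 does not say which comparison tests 14- and 28-day mortality. If the log-rank is run plainly, without strata, its type I error to Day 28 is about 3–4% rather than 5%, and roughly 3–4 points of power are lost. Only the extreme scenario (5% against 70% mortality) brings the error down to 1%.

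A horizon of Day 60 would make the p-value answer a different question from the endpoint. Whether that costs or adds power depends on the effect after Day 28, which is a reason to fix the horizon in advance rather than evidence of a loss.

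The sizes rest on the assumed two-sided 5% level, severity mix, non-ventilated and ECMO mortality, and late hazards, none of which the plan states. The mismatch between a log-rank test and fixed-day endpoints rests on the text alone.

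**What to change.** Add to 9.3.3 item 4, before unblinding:
- the log-rank test is stratified by baseline severity, as in item 1, with sparse levels pooled (for example ECMO with mechanical ventilation, giving scale 5–6 and scale 7);
- it is censored at Day 14 and at Day 28 for the respective endpoints;
- the between-arm difference in Kaplan-Meier mortality at Days 14 and 28 is reported with 95% confidence intervals;
- survival to Day 60 is descriptive.

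The cost is one sentence in the plan. The strata and deaths are already collected, so no new data, visits or patients are needed.
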